## 8. Translational Research / Pharmacodynamic Studies

For instructions on processing and storage of study bloods, vaginome and gut microbiome samples please refer to the study lab manual.

## 9. Data Collection Tool

All data will be handled in accordance with the Data Protection Act. The Case Report Forms (CRFs) will not bear the participant's name or other directly identifiable data. The participant's trial Identification Number (ID) only will be used for identification. The Sponsor Subject ID log can be used to cross reference participant's identifiable information.

Case Report Forms will be designed by the CI and the CI delegate and the final version will be approved by the Sponsor.

It is the Investigator's responsibility to ensure the The Staff Delegation of Responsibilities Log is completed and all data entered and recorded in the CRFs are accurate. The Staff Delegation of Responsibilities Log will identify all trial personnel responsible for data collection, entry, handling and managing the trial Redcap database. Basic demographic and clinical information will be gathered at the time of the initial interview and by review of the medical notes if needed.

All laboratory analysis should be reviewed by the PI and where results reported are not within the normal range the PI must clearly annotate 'Not clinically Significant' or 'Clinically significant' and sign and date the results. The relevant results should be carefully transcribed to the Case Report Forms.

In order to ensure completeness of data collected, participants will be contacted by the research team (telephone call/letter) in the event of missing data such as patient quality of life questionnaires.

### 9.1 Incidental findings

Incidental findings arising during the study will be discussed with the medical and research team involved in the patients care. The medical and research team will always act in the patient's best interest and take appropriate clinical action in accordance with good clinical practice.

### 9.2 Data handling and analysis

Data will be stored in anonymised form in a password-protected database. We will use a customised study database storage programme. Study documentation will be stored for fifteen years after the completion of the study. Quality Control will be applied at each stage of data handling to ensure that all data are reliable and are processed correctly.

## 10. Statistical Considerations

### 10.1 Statistical design

#### Sample size

This is a Phase II open label, single arm study to investigate the activity of oral artesunate in patients with high grade intraepithelial neoplasia CIN2/3 prior to treatment with large loop excision

transformation zone (LLETZ). The primary end point is histological regression of CIN2/3 on colposcopy and biopsy at Day 90.

Significance level and power: The procedure described above tests the null hypothesis that the response rate is 20 % versus alternating hypotheses that the response rate is 50 %. The significance level (i.e., the probability of rejecting H0 when it is true) is  $\alpha=0.1$  and the power (i.e., 1-beta, the probability of deciding the regimen is active) is 90% when true response rate is 50 %.

At the significance level of 0.05, with an equivalence limit of 0.15, a sample size of 24 is required to achieve 90% power when the response rate for the historical control is 0.2 and response rate for the treatment is 0.5.

Inflating this sample size by 20% to allow for loss at follow-up would result in approximately 28 patients. We believe that 28 patients represents a feasible and achievable target given our time and financial considerations.

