To determine the effect of artesunate on the vaginome and gut microbiome	Comparison of vaginome and gut microbiome at Day 0, Day 64 and Day 90														
To determine the effects of artesunate on patient safety	Serious Adverse Event at 90 days using Common Toxicity Criteria (CTCAE V5.0)														
To determine the effects of artesunate on patient Quality of Life	Quality of life using the European Quality of Life-5 Dimensions (EQ-5D) quality of life tool														
Study design	Phase II open label single arm study														

Number of patients (statistical design)	A maximum of 28 participants will be enrolled to receive the study intervention. The primary end point is histological regression of CIN2/3 on colposcopy and biopsy at Day 90. Significance level and power: The procedure described above tests the null hypothesis that the response rate is 20 % versus alternating hypotheses that the response rate is 50 %. The significance level (i.e., the probability of rejecting H0 when it is true) is $\alpha=0.1$ and the power (i.e., 1-beta, the probability of deciding the regimen is active) is 90% when true response rate is 50 %. At the significance level of 0.05, with an equivalence limit of 0.15, a sample size of 24 is required to achieve 90% power when the response rate for the historical control is 0.2 and response rate for the treatment is 0.5. Inflating this sample size by 20% to allow for loss at follow-up would result in a sample size of approximately 28 patients.

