#### Withdrawal of consent from the participant

As participation in the trial is entirely voluntary, the participant may choose to discontinue treatment at any time without penalties or loss of benefits to which they may be entitled. Although not obliged to give a reason for discontinuing their trial treatment/study participation a reasonable effort should be made to establish this reason, whilst remaining fully respectful of the participant's rights. Participants who discontinue protocol treatment, for any of the above reasons, should remain in the trial for the purpose of follow up and data analysis.

Temporary discontinuations of study medication are not permitted. If a patient decides to discontinue treatment then the patient's decision should be documented on the Subject Tracking log, CRF and the IMP returned to the study site Pharmacy or research centre. Participants should continue to be followed up as closely as possible to the follow-up schedule defined in the protocol, providing they are willing. However if the participant confirms they do not wish to participate in the scheduled follow up data collection visits then data that has already been collected should be kept and analysed according to the ITT principle for all participants who stop follow up early. Patients withdrawn from the study will continue to be followed up according to the study protocol to the scheduled date of study completion, or to recovery or stabilisation of a followed-up Adverse Events (AE), whichever comes last. Routine medical and surgical care of withdrawn participants will continue as planned. The investigator will make every effort to contact the participant in the case of non attendance to a planned review appointment. Participants who stop the trial follow up early will not be replaced.

Participants who develop CTCAE v5.0 Grade 3 or 4 serious adverse effects related to artesunate will be withdrawn from the study treatment but will continue in the study to enable an intention to treat analysis.

There will be a 24 hour emergency card provided to each participant when they receive their IMP dispensed from pharmacy. The 24 hour emergency card will contain the contact details of the local PI and site team in addition to a NeoART-CIN 24 hour emergency telephone number.

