### **10.1.1 Interim analyses / Decision rules**

An interim analysis reviewing feasibility and tolerability will be performed once 10% (n = 3) and 50% (n = 14) of patients have completed their day 90 assessments. No early conclusions will be drawn.

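### Enrolling 28 is about 17% above the required 24, not 20%, and keeps 24 patients with Day 90 histology only if at most 4 (14.3%) are lost

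*Protocol*

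**What the plan says.** Section 10.1 of the Protocol (Sample size) states that "a sample size of 24 is required to achieve 90% power". The calculation assumes regression in 20% of historical controls and in 50% of treated patients. It then adds an allowance for loss: "Inflating this sample size by 20% to allow for loss at follow-up would result in approximately 28 patients". The Protocol Summary, under the number of patients, repeats this almost word for word: "Inflating this sample size by 20% to allow for loss at follow-up would result in a sample size of approximately 28 patients".

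Three other statements bear on how the allowance works:

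- The Protocol Summary makes 28 a ceiling: "A maximum of 28 participants will be enrolled to receive the study intervention".
- Section 5.3, on withdrawal of consent, rules out topping up: "Participants who stop the trial follow up early will not be replaced".
- Section 10.1 defends 28 on practical grounds as well: "We believe that 28 patients represents a feasible and achievable target given our time and financial considerations".

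**The concern.** The stated percentage and the stated total do not match. A reader of Section 10.1 will take it that the trial can absorb a 20% loss and still have the 24 patients on which the power statement rests. With a ceiling of 28 and no replacement, a shortfall cannot be made up during the trial, so the margin is whatever 28 provides at the outset. This sentence is the only numerical allowance for loss in the Protocol. At stake is whether the stated 90% power still holds at the loss rate the plan appears to provide for.

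**Working it through.** **Inputs from the Protocol.** Required number 24, inflation 20%, response rates 0.2 and 0.5, power 90%, and significance levels 0.05 and 0.1 (Section 10.1); maximum enrolment 28 (Protocol Summary); no replacement (Section 5.3).

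**Assumption.** The Protocol does not say whether its levels are one-sided or two-sided. One-sided 0.05 is assumed because it reproduces 24. Results at one-sided 0.10 are shown beside it because Section 10.1 also gives 0.1.

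**Step 1: the plan's 24.** One-sample normal formula with the variance at the alternative, leaving aside the 0.15 limit that Section 10.1 also mentions:

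n = p1(1 - p1)(z_alpha + z_beta)^2 / (p1 - p0)^2 = 0.25 x (1.645 + 1.2816)^2 / 0.3^2 = 23.8, rounded up to 24. The plan's figure is reproduced.

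**Step 2: the plan's 28.**

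- Multiplying up: 24 x 1.20 = 28.8. Rounding down gives 28; rounding up gives 29.
- Allowing for a 20% loss: 24 / (1 - 0.20) = 30.
- Inflation delivered by 28: 28/24 - 1 = 16.7%.

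So 28 is the first calculation rounded down, and it falls short of 20% on either reading.

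**Step 3: the loss that 28 tolerates.**

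- 28 - 24 = 4 patients, and 4/28 = 14.3%.
- A 20% loss from 28 is 28 x 0.20 = 5.6 patients, leaving 28 x 0.80 = 22.4, or about 22.
- For comparison, 29 would tolerate 5/29 = 17.2%, and a 20% loss from 29 leaves 29 x 0.80 = 23.2.

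**Step 4: what this does to power.** Exact binomial test of 0.2 with true rate 0.5. The cut-off is the smallest number of responders that keeps the type I error at or below the level.

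| Patients with Day 90 data | Level (one-sided) | Cut-off | Actual type I error | Power |
|---|---|---|---|---|
| 24 | 0.05 | 9 | 0.036 | 92.4% |
| 23 | 0.05 | 9 | 0.027 | 89.5% |
| 22 | 0.05 | 9 | 0.020 | 85.7% |
| 24 | 0.10 | 8 | 0.089 | 96.8% |
| 23 | 0.10 | 8 | 0.072 | 95.3% |
| 22 | 0.10 | 8 | 0.056 | 93.3% |

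Power moves in steps because the cut-off is a whole number. At one-sided 0.05, 22 is a local low point: with 21 patients the cut-off falls to 8 and power is 90.5%. A single row therefore slightly exaggerates the effect. If each patient had an independent 20% chance of loss, which is an assumption, power at one-sided 0.05 averaged over the number retained would be 89.0% with 28 enrolled and 90.1% with 29. At one-sided 0.10 it would be 93.9% with 28.

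**The case against.** The strongest reply is that the Protocol calls 28 approximate. It lies 0.8 of a patient below 28.8, and Section 10.1 then accepts it for reasons of time and money. That stands: 28 is a rounded-down result that the plan chose to adopt, not a wrong sample size.

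A second reply is that inflating by 20% does not predict that 20% will be lost. That also stands. The figures for 22 patients and the averaged powers are conditional on a loss rate that the Protocol does not state. The limit of 4 losses needs no such assumption.

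A reader might infer more than the documents support:

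- **That 29 is the correct number.** It is 28.8 rounded up, but it does not cover a 20% loss either. That would take 30, and nothing in the Protocol settles which meaning of 20% was intended.
- **That Section 10.1.1 shows 28 to be exact.** The interim reviews are set "once 10% (n = 3) and 50% (n = 14) of patients have completed their day 90 assessments". Half of 28 is 14, but 10% of 28 is 2.8, given as 3. That section rounds to whole patients too, so it proves nothing about exactness.
- **That this sentence is the only provision for loss.** It is only the numerical one. Section 5.7 provides for repeated contact after a missed visit, Section 5.3 keeps patients who stop treatment in follow-up, Section 9 provides for contact about missing data, and the Day 90 visit coincides with standard-of-care excision (Sections 5.8 and 6.3).

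None of these replies makes 28 a 20% inflation of 24.

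**Conclusion.** The point holds as a minor correction to a stated figure. Enrolling 28 is 16.7% above 24, and with the cap and no replacement it preserves 24 patients with Day 90 histology only up to 4 losses (14.3%). These results follow from the Protocol's own numbers.

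The consequence for power is small and rests on two assumptions: a 20% loss, and one-sided testing. About 22 patients would give roughly 86% power at 0.05, below the 90% target, and roughly 93% at 0.10, above it. A reader might infer that the trial is underpowered or must enrol more patients. The documents do not support that: the shortfall appears only if losses exceed 4, and even then it is a few percentage points at one level and absent at the other.

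**What to change.** Keep 28 and restate the allowance in Section 10.1 and in the Protocol Summary, for example: *28 enrolled is about 17% above 24 and retains 24 patients with Day 90 histology if no more than 4 (14%) are lost.*

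The cost is one sentence in each of two places. No patients are added, and the analysis, the cap and the no-replacement rule are unchanged.

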### **10.1.1 Interim analyses / Decision rules**

An interim analysis reviewing feasibility and tolerability will be performed once 10% (n = 3) and 50% (n = 14) of patients have completed their day 90 assessments. No early conclusions will be drawn.

### **10.1.2 Accrual and Duration of Study**

The estimated accrual for this study is 3 patients a month. Thus, patient accrual is expected to be completed within 24 months. An additional 6 months is required to allow the response data to mature.

## **10.2 Statistical Analysis**

The study outcome measures are listed in chapter 2. The methods used to evaluate them are detailed in this section. The statistical analysis will be performed using *SAS® and Graphpad software*.

### **10.2.1 Analysis populations**

- ◆ Intention-to-treat population: All patients will analysed according treatment allocation.
- ◆ Per protocol population: All patients who meet the eligibility criteria and have started their allocated treatment (at least 8 out of 14 doses in cycle 1 of their treatment plan).

Safety population: All patients who have started protocol treatment (e.g., at least one dose of the study drug).

### **10.2.2 Patient disposition, data recording and display**

Patients' demographics, baseline characteristics, prior and concomitant medications, treatment exposure, protocol compliance and study withdrawals will be summarized in the intent-to-treat population. For categorical variables, frequency tables (with %) will be presented with descriptive listings of details specified in text fields, when appropriate. Continuous variables will be reported using median, range and interquartile range.

A CONSORT diagram will be used to document the flow of patients through the various stages of the study. The number of patients included in the various analysis populations will be presented in a table and reasons for exclusions will be detailed in listings.

### **10.2.3 Safety**

Safety analyses will be performed on the safety population. Patients will be analysed according to the treatment actually started, regardless of duration or compliance with treatment.

#### **Periods**

- "Baseline" is defined as the period from before study entry to first day of protocol treatment administration. For patients who never started treatment, the baseline period is assumed to end on the day of enrolment.
- "On treatment" is defined as the time on study after baseline (i.e., starting on the first day of protocol treatment administration) to and including 30 days after the day of last protocol treatment administration.
- "Follow-up period" is defined as the period that follows the on-treatment period until the end of the follow up. For patients who never started treatment, the follow-up period is assumed to start on the day of enrolment.

#### **10.2.3.1 Safety analyses**

Tables on AEs will report

- all AEs irrespective of their relationship to treatment
- the AEs related to the treatment (excluding those declared not reasonably possibly related to the treatment, but including those with relationship not assessable).

The worst grade of the AEs per patient and per CTCAE term over each period will be tabulated by treatment arm. The percentage of patients on each treatment arm presenting severe treatment-related AE (grade  $\geq 3$ ), of patients reported to have died of toxicity and that of patients who stopped treatment due to toxicity will also be calculated and the 95% confidence interval will be presented.

For the reporting of SAEs:

- the study safety overview table will list the number of reported SAE terms, SAR terms and SUSAR terms per treatment arm and the number of reported death and toxic death cases;
- line listings of SAEs and of SARs will be provided;
- the number of SAEs and SARs per System Organ Class and Preferred Term will be tabulated

### **10.2.4 Study outcome measures**

Primary outcome measure(s)

- Histological regression of CIN2/3 on colposcopy and biopsy at Day 90 will be defined as histologic regression to CIN1 or less. This will be described as a response percentage.

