## 1.2 Outcome measures

#### 1.2.1 Primary outcome measure

- Histological regression of CIN2/3 on colposcopy and biopsy at Day 90.
  - Histological regression will be defined as histologic regression to CIN1 or less.

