### **3. Trial Design**

This is a Phase II single arm, open label study of artesunate to determine the feasibility, safety and preliminary anti-proliferation activity of oral artesunate in HPV +ve High Grade Cervical Intraepithelial Neoplasia (CIN2/3). Patients with HPV positive CIN2/3 will receive 3 cycles of oral artesunate 200mg OD prior to standard of care therapeutic large loop excision transformation zone (LLETZ). Each 21 day treatment cycle will comprise oral artesunate 200mg OD for 14 days followed by a 7 day treatment break. Patients will be followed up clinically after each cycle of treatment till standard of care large loop excision transformation zone (LLETZ) at 90 days. Colposcopy and cervical biopsy to assess histological regression will be performed at 90 days. A cervical sample to test for HPV DNA clearance will also be collected. A vaginal swab will also be collected for vaginome analysis and a faecal sample collected for microbiome analysis.

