#### **4.1 Inclusion criteria**

- Aged 18 or over
- Histologically proven HPV positive cervical CIN2/3
- WHO performance status 0-2
- Adequate full blood count:
  - White Cell Count (WCC)  $>3.0 \times 10^9 /l$ ;
  - Platelets  $>100 \times 10^9 /l$ ;
  - Haemoglobin (Hb)  $>80g/L$
- Adequate renal function:
  - Glomerular Filtration Rate  $>30ml/min$
- Adequate hepatobiliary function:
  - Total bilirubin  $< 3 \times$  Upper limit normal

- Female participants of child bearing potential must have a negative pregnancy test < 72 hours prior to initiating study intervention and agree to avoid pregnancy using adequate, medically approved contraceptive precautions for up to 6 weeks after the last dose of study treatment intervention
- Patient able and willing to provide written, informed consent for the study

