# 6. Clinical Evaluation, Laboratory Tests, Follow-Up

## 6.1 Before treatment start

The following information will be recorded for all subjects up to 7 days prior to starting study treatment on D1(-7 days):

- Demographic details: Date of consent, enrolment, age, ethnicity, HPV vaccination status
- Clinical data: symptomatology, weight, height, vital signs
- Colposcopy findings (within 28 days of study commencement)
- Histology: routine histological grading (within 28 days of study commencement)
- HPV DNA oncotyping (within 28 days of study commencement)
- Concomitant medication: all non-study drugs taken will be recorded

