#### **Day 90 (+ 14 days)**

- Clinical Assessment
- Safety blood test – FBC, U&E, LFT
- Study blood test (plasma & PBMC)
- Colposcopy & endocervical biopsy
- HPV DNA oncotyping
- Vaginome and gut microbiome sampling
- Large Loop Excision Transformation Zone
- Quality of Life Tool (European Quality of Life–5 Dimensions (EQ-5D))

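### Response rests on the Day 90 colposcopy and biopsy alone, so a patient can count as regressed even if tissue excised at the same visit still shows CIN2/3

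*Protocol*

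**What the plan says.** Protocol section 4.1 admits patients with "Histologically proven HPV positive cervical CIN2/3". Section 6.1 lists the baseline assessment as "Histology: routine histological grading (within 28 days of study commencement").

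Section 1.2.1, section 10.2.4 and the synopsis give the same response rule: "Histological regression of CIN2/3 on colposcopy and biopsy at Day 90 will be defined as histologic regression to CIN1 or less". Section 10.2.4 and the synopsis add: "This will be described as a response percentage". This is one figure for CIN2 and CIN3 together.

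Section 3 describes a single-arm trial with one post-treatment histology time point: "Colposcopy and cervical biopsy to assess histological regression will be performed at 90 days". The Day 90 list in section 6.3 has "Colposcopy & endocervical biopsy" and, as a separate item, the large loop excision. Section 5.8 also places the excision at Day 90. Neither the endpoint definition nor section 10.2.4 says that histology of the excised specimen plays any part in response.

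The number of biopsies, the number of readers and any second or central reading are not stated. Section 10.1 tests a 20% response rate against 50%. Section 2.1 gives 20% to 40% spontaneous regression for CIN2-3 as a group.

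**The concern.** Entry and response meet at the same CIN1/CIN2 boundary. Patients are selected on a reading above it and scored as responders on a later reading below it. A biopsy that misses the remaining lesion, or is graded too low, produces a response without any change in the disease. A baseline CIN2 needs a one-grade error for this and a baseline CIN3 needs two, yet both count equally.

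In a randomised trial such errors would fall on both arms. Here there is no concurrent control, so they add directly to the rate that is compared with a fixed 20%.

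The trial removes the transformation zone at the same visit. Histology of that specimen could show whether a lesion read as regressed on biopsy was still present. As the endpoint is written, a patient whose excised tissue shows CIN2/3 is still a responder if the biopsy reads CIN1 or less. At stake is whether a rate above 20% can be read as regression.

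**Working it through.** **1. Plan's own figure.** Inputs from section 10.1: null 0.20, alternative 0.50, alpha 0.05, power 90%, N = 24. A one-sample normal approximation with the variance at the alternative and one-sided alpha gives

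n = ((1.645 + 1.282) × √(0.5 × 0.5) / 0.30)² = 23.8, so 24.

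The stated 24 reproduces without using the 0.15 limit.

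**2. Decision rule.** The protocol states none, so I take the smallest exact binomial cut-off that holds the level.
- At one-sided 0.05 with n = 24: at least 9 responders. P(X ≥ 9 | 24, 0.20) = 0.036 and P(X ≥ 9 | 24, 0.50) = 0.924.
- At 0.10, the other level in section 10.1: at least 8 responders, with actual level 0.089 and power 0.968.

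**3. Effect of false regression (assumed).** Let p = 0.20 be the true no-effect regression rate and m the share of true non-responders read as CIN1 or less. True regressions are taken as read correctly. Then

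apparent rate = p + (1 − p) × m.

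- m = 5%: 0.20 + 0.80 × 0.05 = 0.24
- m = 10%: 0.20 + 0.80 × 0.10 = 0.28

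Probability of a positive result with no drug effect, P(X ≥ r | n, apparent rate):

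| Rule | m = 0 (20%) | m = 5% (24%) | m = 10% (28%) |
|---|---|---|---|
| ≥ 9 of 24 | 0.036 | 0.099 | 0.206 |
| ≥ 8 of 24 | 0.089 | 0.199 | 0.351 |

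The values of m are assumptions; the documents offer no figure for them.

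**4. Error alone, with no true regression.** Take a latent grade spread evenly from 0.5 to 3.5 and normal reading error with SD 0.3 to 0.6 grade. Entry is a baseline reading of at least 1.5, response is a Day 90 reading below 1.5, and nothing truly changes. Then 8.5% to 16.4% of enrolled patients respond. If every lesion is truly CIN2 or worse (latent grade from 1.5), this falls to 4.5% to 9.6%. Both ranges lie below 20%. At 8.5% to 16.4%, P(X ≥ 9 | 24) is about 0.0001 to 0.011. Error becomes a threat only when it adds to genuine spontaneous regression, as in step 3.

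**5. Precision by grade.** With 28 patients and an even mix (assumed), each grade has 14. The exact 95% interval for 7 of 14 runs from 23% to 77%, so grade-specific rates can only describe.

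**The case against.** **The threshold is sound.** CIN1 or less is a coherent definition of regression from CIN2/3 and is not itself an error. This stands, and the fix leaves it alone.

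**A single reading is not stated.** A reader might infer that the plan prescribes one reading of one biopsy. The protocol is silent on the number of biopsies and readers, so only the absence of a specified confirmation can be claimed.

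**Noise alone does not make a positive trial.** A reader might infer that grading error by itself could carry the result. Step 4 shows otherwise, and its inputs are assumed as well.

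**The 20% may already contain the error.** If the historical rate came from biopsies with similar sampling and reading error, part of the inflation is already in the null. The documents do not show how that rate was obtained, so the effect in step 3 is an upper reading for each m.

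**Dependence on grade mix is not documented.** A reader might infer that the response rate is known to shift with the CIN2:CIN3 mix. Unequal distances to the cut-off make this plausible, but the 20% null and the 20% to 40% background figure are both pooled. Section 10.2.2 summarises baseline characteristics, which would probably include the grade recorded under section 6.1, so it cannot be said that the mix goes unreported.

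**A split by grade is SAP-level reporting.** This largely stands; absence of the split is no defect on its own. What remains is the response rule that the protocol itself states, which leaves out the excised specimen.

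**Conclusion.** The point holds in limited form. The protocol defines response on the Day 90 colposcopy and biopsy, with entry and response meeting at one boundary, grades pooled, no control arm and no confirmation specified. It does not use the specimen excised at the same visit. As written, persisting CIN2/3 in that specimen does not prevent a patient from counting as regressed.

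The size cannot be taken from the documents. Under the assumption of 5% to 10% false regression among true non-responders, on top of a true 20%, the false-positive probability for at least 9 of 24 goes from 0.036 to about 0.10 to 0.21. It is less if the historical 20% shares the error. This deserves a change of wording but does not invalidate the primary endpoint.

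**What to change.** Keep the primary definition. Add to section 10.2.4 and the synopsis:

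- A prespecified supportive analysis in which response requires CIN1 or less on both the Day 90 biopsy and the histology of the excised specimen. State how a patient without one of the two results is counted.
- The primary response rate by recorded baseline grade (CIN2, CIN3), each with an exact 95% confidence interval, labelled descriptive only.

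The grade-specific rates should not be tied to the overall claim, because no threshold would govern how they are weighed. No set reduction in false responders should be promised from the second specimen either. Errors in two samples of the same lesion at the same visit may be correlated, and the gain shrinks if they are.

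Cost: wording, with no new visit or procedure. This assumes that the excised tissue is examined histologically as part of routine care, which the protocol does not spell out; the result would have to be captured on the case report form. The confirmed rate will be somewhat lower than the biopsy rate, and the grade-specific intervals will be wide, with about 14 patients per grade if the mix is even.
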